### **3.5 Discontinuation of Subjects from Treatment**

Subjects MUST discontinue investigational product (and non-investigational product at the discretion of the investigator) for any of the following reasons:

- Subject's request to stop study treatment
- Any clinical adverse event (AE), laboratory abnormality or intercurrent illness which, in the opinion of the investigator, indicates that continued participation in the study is not in the best interest of the subject
- Pregnancy
- Termination of the study by Bristol-Myers Squibb (BMS)
- Loss of ability to freely provide consent through imprisonment or involuntarily incarceration for treatment of either a psychiatric or physical (eg, infectious disease) illness
- Missing 2 consecutive belatacept infusions, unless the subject is receiving lymphocyte-depleting therapy or has approval by the medical monitor to remain in the study. Documentation will be required.
- Subjects who have met protocol defined criteria for graft loss ([Section 5.3.12](#))

All subjects who discontinue investigational product should comply with protocol specified Early Termination (ET) and follow-up procedures as outlined in [Section 5](#). Information on subject and allograft survival will be collected for all subjects through 24 months post-transplant. The only exception to this requirement is when a subject withdraws consent for all study procedures including post-treatment study follow-up or loses the ability to consent freely (ie, is imprisoned or involuntarily incarcerated for the treatment of either a psychiatric or physical illness).

If study treatment is discontinued prior to the subject's completion of the study, the reason for the discontinuation must be documented in the subject's medical records and entered on the appropriate case report form (CRF) pages.

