### **3.6 Post Treatment Study Follow up**

Withdrawal of a subject from study medication does not imply that the subject is withdrawn from the study. Early Termination (ET) and Follow-Up Safety visit procedures must be completed per [Table 5.1-3](#) for all subjects who discontinue study drug. Information on subject and allograft survival will be collected for all subjects through 24 months post-transplant (at 6, 12 and 24 months).

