#### **5.3.7 Assessment of Clinical Suspicion of Acute Rejection**

In this protocol, acute rejection is defined as a clinical (“clinically suspected”) and pathological (biopsy proven) event. In addition to identification, on an allograft biopsy, of findings consistent with either cell- or antibody-mediated acute rejection, confirmation requires that at least one of the clinical criteria listed below be met:

- An unexplained increase in serum creatinine concentration of  $\geq 25\%$  from a recent baseline value.

*“Recent baseline” serum creatinine is defined as the average of the 3 most recent serum creatinine concentrations that were available prior to the value that prompted clinical suspicion of acute rejection and were determined by a local laboratory. These 3 serum creatinine concentrations must have been obtained from samples drawn on different days and prior to initiation of the first treatment in any course of dialysis that the subject receives.*

- An unexplained decrease in urine output
- Fever and allograft tenderness that is otherwise clinically unexplained
- During the first 14 days post-transplant, an otherwise unexplained, persistent elevation in serum creatinine in the presence of clinical suspicion of acute rejection

OR

- Acute rejection that is: (a) clinically suspected for any other reason(s); and (b) is treated.

Unless a biopsy is medically contraindicated due, for example, to a risk of hemorrhage that cannot be satisfactorily mitigated by administration of fresh frozen plasma or plasma factor concentrates, no subject should be treated for AR without having a biopsy performed to confirm the diagnosis. If a subject is treated for AR without biopsy confirmation, this should be clearly indicated on the appropriate CRF pages.

Prior to obtaining any biopsy for suspected AR, the presence of other clinical conditions that could adversely affect renal function should be ruled out, including those affecting the patency of the renal artery and vein, obstruction (hydronephrosis), intravascular volume depletion, infection and drug-associated nephrotoxicity.

Notes:

- ◆ Acute rejection will not be reported as an AE or SAE in this study, see [Section 6](#). These events will be collected on separate CRFs.
- ◆ Routine or surveillance biopsies performed according to local practice and in the absence of clinical suspicion of acute rejection are NOT permitted per protocol.

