### **5.3.12     *Definition of Graft Loss***

In this study, graft loss is defined as either functional loss or physical loss. Functional loss is defined as meeting any of the criteria:

- Regularly scheduled or chronic dialysis treatments over a period of  $\geq 56$  days.
- Re-transplantation (either preemptive or if first criterion above is met and subject is waiting for transplant).

Physical graft loss is defined as surgical excision (nephrectomy).

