#### **8.4.2.3    *Renal Function***

Calculated GFR at Months 3, 6, 12, and 24 and change in cGFR from Month 3 to Months 6, 12 and 24, respectively, will be descriptively summarized. For a subject who has one or more missing values for cGFR due to a graft loss or death, the missing values will be imputed as “zero”.

A linear mixed effects model will be used to analyze changes from Month 3 cGFR. Details of the analyses will be available in the Statistical Analysis Plan.

Population-mean slopes will be estimated for each treatment group. In addition, the 95% confidence intervals will also be obtained for each mean slope. Intercepts will be summarized in the same manner.

In addition, urinary protein to creatinine ratios, to be obtained from single-voided urine specimens at 3, 6, 12 and 24 months post-transplant, will be descriptively summarized.

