7.6.2.3 Renal Function

The following table provides a summary/overview of the analysis performed.

Table 7.6.2.3-1: Overview of Analysis: Renal Function

Renal Function variable	Analysis	Time points for analysis
cGFR using MDRD formula	Descriptive summary of absolute values for each Treatment group	Month 3, 6, 12, 24
	Descriptive summary of change from Month 3 values for each Treatment group	Month 6, 12, 24
	Fixed Effects repeated measure model using Time and Treatment as class variables and Month 3 cGFR as a covariate	Month 6, 12, 24
	Mixed effects using Time as random variable and Treatment as class variable. Analysis on absolute cGFR value using Month 3 cGFR as a covariate	Month 6, 12, 24
Urine protein/ creatinine ratio (U _{PR} /CR)	Descriptive summary of absolute values for each treatment group	Month 3, 6, 12, 24
	Descriptive summary of change from Month 3 values for each Treatment group	Month 6, 12, 24
	Fixed Effects repeated measure model using Time and Treatment as class variables and Month 3 cGFR as a covariate	Month 6, 12, 24

cGFR

Calculated GFR at Months 3, 6, 12, and 24 and change in cGFR from Month 3 to Months 6, 12 and 24, respectively, will be descriptively summarized.

A linear mixed effects model will be used to analyze changes from Month 3 cGFR. The linear mixed model for repeated measures with terms of Month 3 cGFR values, treatment, month, and interaction of treatment by month. The variable month will be categorical. The unstructured (UN) covariance structure will be assumed. If computation convergence becomes an issue, the compound symmetric (CS) covariance structure will be used. For each time point, the difference between treatment arms will be calculated along with the corresponding 95% confidence intervals.

Population-mean slopes will be estimated for each treatment group. In addition, the 95% confidence intervals will also be obtained for each mean slope. Intercepts will be summarized in the same manner. This analysis will be based on a linear mixed model including terms for treatment, Month 3 cGFR, treatment-by-month interaction as well as month (continuous covariate) as fixed effects. The model will also include a random intercept and slope for month. Unstructured covariance structure will be used.

For all of the analyses above, for any subject who has one or more missing values for cGFR due to a graft loss or death, the missing values will be imputed as “zero”.

Urine Protein/Creatinine Ratio

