8.3 Missing Data Handling

The following conventions will be followed while handling missing data. Only the relevant endpoints along with the specifics of the convention are included in this section.

Subject Survival and Graft Survival

Any subject (either randomized to belatacept or CNI) with unknown subject and graft survival status at Month 12 or Month 24, that is, whose last known follow-up date occurred prior to Day 334 or Day 698, respectively, will be considered as having experienced an event of graft loss or death, if at least one of the following criteria have been met during their documented period of follow-up post-randomization:

- Subject experienced at least one episode of BPAR at the time of, or prior to the last follow-up date.
- Subject was diagnosed as having PTLD at the time of, or prior to the last follow-up date.
- Subject's reason for discontinuation of study medication was lack of efficacy.
- A diagnosis of biopsy confirmed Polyomavirus associated nephropathy was reported as an adverse event before discontinuation.
- Subject's last calculated GFR (4-variable MDRD equation) was $< 15\text{mL}/\text{min}/1.73\text{m}^2$.

The remaining subjects with unknown patient and/or graft survival status at Months 12 or 24 (those who do not meet any of the above criteria) will be considered missing and not be included in the analyses or listing of the death and graft loss. For example, a patient with unknown status of the graft function and patient survival, and with no records of the above mentioned criteria, will not be considered in the numerator or denominator, while computing the percentage of death or graft loss.

Acute Rejection

Any acute rejection-free subject who is not followed-up through the entire event-counting period due to any reason will be considered as having no acute rejection during that period.

Renal Function

Missing cGFR values due to death or graft loss will be imputed with value of 0 and all other missing values will remain missing.

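### The cGFR zero rule reaches only missing values, so a creatinine measured on or after graft loss can be kept as study-graft function (minor correction)

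*SAP*

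**What the plan says.** The rule appears three times with the same scope.

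- SAP 7.6.2.3 applies it to all the cGFR analyses listed there (summaries, changes from Month 3, the repeated-measures model and the slopes). For any subject with "one or more missing values for cGFR due to a graft loss or death, the missing values will be imputed as" zero.
- SAP 8.3: "Missing cGFR values due to death or graft loss will be imputed with value of 0 and all other missing values will remain missing".
- Protocol 8.4.2.3: "For a subject who has one or more missing values for cGFR due to a graft loss or death", again zero.

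SAP 8.4 assigns results to time points by study day rather than nominal visit. If a window holds several results, the one nearest the target day is used. It has no exclusion for dialysis, graft loss or ET draws.

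Protocol 5.3.12 counts as functional graft loss "Regularly scheduled or chronic dialysis treatments over a period of" at least 56 days, and also re-transplantation. Section 3.5 lists "Subjects who have met protocol defined criteria for graft loss" among the reasons for mandatory discontinuation of investigational product. Section 3.6 then requires that "Early Termination (ET) and Follow-Up Safety visit procedures must be completed per" Table 5.1-3. Beyond those visits, 3.6 names only subject and allograft survival, at 6, 12 and 24 months.

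**The concern.** cGFR here is the creatinine-based 4-variable MDRD value. Creatinine drawn on dialysis partly reflects dialysis clearance, and after re-transplantation it reflects another kidney. Neither measures the study graft. The protocol guards against the first problem in one place: in 5.3.7 the creatinines that form the recent baseline for suspected rejection must be drawn "prior to initiation of the first treatment in any course of dialysis that the subject receives". The cGFR analysis has no counterpart.

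The SAP chose zero to represent a failed graft, but its wording delivers zero only when no result exists. Two subjects with the same graft loss can score 0 and a positive number, depending on whether blood was drawn inside a window. Retained positive values overstate function in the arm with more graft loss. If the loss is early, a retained value can also become the Month 3 covariate and the reference for later changes. This is separate from whether zero is the right value for a failed graft.

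**Working it through.** The plan states no figure on this point, so there is none to reproduce. The check has three parts: what a retained value would be, how far it moves an arm mean, and how often it could arise.

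**Inputs from the documents.** 35 subjects per arm (SAP 2.1). Windows in SAP 8.4: Month 3, days 57-112; Month 6, 141-196; Month 12, 337-392; Month 24, 701-756. ET visit within 14 days of discontinuation, or as soon as possible after that (protocol Table 5.3.2-1).

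**Assumed inputs.** cGFR = 175 x SCr^-1.154 x age^-0.203, times 0.742 if female and 1.212 if Black. A constant of 186 instead of 175 raises every value by 186/175, about 6%. Creatinine is taken as 4 to 10 mg/dL on dialysis and 1.2 to 2.0 mg/dL after re-transplantation.

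**Retained value (constant 175; first two columns age 50, non-Black).**

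| Creatinine, mg/dL | Male | Female | Ages 18-75, both sexes, both race terms |
|---|---|---|---|
| 4 (dialysis) | 16.0 | 11.9 | 10.9 to 23.8 |
| 6 (dialysis) | 10.0 | 7.4 | 6.8 to 14.9 |
| 8 (dialysis) | 7.2 | 5.3 | 4.9 to 10.7 |
| 10 (dialysis) | 5.5 | 4.1 | 3.8 to 8.3 |
| 1.3 (re-transplant) | 58.4 | 43.4 | 39.9 to 87.1 |
| 2.0 (re-transplant) | 35.5 | 26.4 | 24.3 to 53.0 |

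With the 186 constant, the value at 4 mg/dL reaches 25.3. On-dialysis values therefore run from about 4 to 25 and are often below 10. Values near 60 arise only after re-transplantation, at about 1.3 mg/dL in a man of 50. That is a reference case, and the last column shows how far other recipients differ.

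**Shift in an arm mean** = retained value / 35, since the intended score is 0.

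- Dialysis: 4/35 = 0.11 to 25/35 = 0.71 mL/min per subject.
- Re-transplantation at 60: 60/35 = 1.71.
- Two dialysis subjects in one arm: 2 x 4/35 = 0.23 to 2 x 25/35 = 1.43.

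**How often one ET draw lands in a window.** Take the draw as equally likely on any day from 57 to 728. The windows cover 56 + 56 + 56 + 28 = 196 of those 672 days, or 29%. SAP 8.4 narrows Month 3 to days 71-112 if Week 8 data are collected, as Table 5.1-2 appears to schedule for chemistry. Coverage is then 42 + 56 + 56 + 28 = 182 of 672, or 27%. The nearest-to-target rule can also replace the ET value with an earlier scheduled one.

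**Average effect per failed graft on dialysis, one ET draw:** 0.29 x 0.11 = 0.03 to 0.29 x 0.71 = 0.21 mL/min on the arm mean.

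**The case against.** The strongest reply is that the protocol already makes most values after graft loss missing, and hence zero. Graft loss forces discontinuation. One ET visit follows, then a safety visit that may be by telephone and lists no creatinine (5.3.17), and after that only survival status is named. This stands, and it limits the usual exposure to about one draw. It does not remove the gap. Sections 4.3.3 to 4.3.5 keep subjects who stop for intolerance in protocol-specified follow-up without saying which laboratory tests that includes, and nothing tells a programmer to discard a result that exists.

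A reader might infer from Table 5.1-3 that an ET cGFR certainly exists, because creatinine is marked at M24/ET. That row is under local laboratories, whereas protocol 5.3.6.1 lists cGFR with the central chemistry panel, whose Year 2 row is not readable in our copy. A Month 24 cGFR endpoint makes a central draw in that column likely, but it is not shown.

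Three other stronger readings are tempting, and the documents do not support them:

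- **A failed graft is routinely scored 10 to 60.** This needs a draw that falls in a window. Dialysis values can be below 10, and 60 needs a draw after a new graft.
- **On-dialysis values before graft loss should be set to missing.** That deletes the lowest values. If the other 34 subjects average 55 (assumed), dropping a 7 raises the mean by (55 - 7)/35 = 1.4, and dropping a 22 by (55 - 22)/35 = 0.9. Both exceed the 0.1 to 0.7 at issue.
- **The SAP 8.3 criterion of last cGFR below 15 fails for the same reason.** It applies only when survival status is unknown. Escaping it needs an on-dialysis subject with no documented graft loss, then lost to follow-up, with creatinine below about 4.2 mg/dL (man of 50) and none of the other four criteria met.

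Protocol 5.3.7 concerns the diagnosis of rejection. It shows awareness of the dialysis problem but is not a rule about cGFR.

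**Conclusion.** The gap is real and small. All three visible statements of the rule stop at missing values, and the windowing rule would admit a measured one. Identical graft losses can therefore be scored differently.

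The size is about 0.1 to 0.7 mL/min on a 35-subject mean per affected dialysis subject, and about 1.7 for a retained value near 60 after re-transplantation. A single ET draw has at most about a 30% chance of entering a window. These figures rest on assumed creatinine values, assumed MDRD coefficients and evenly spread timing of the draw. The number of graft losses is not known from the documents.

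cGFR is a secondary endpoint, and SAP 7.2 specifies no statistical tests, so no formal conclusion depends on this. Parts of the SAP are redacted, including the text just before 8.2, and an override there cannot be excluded.

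**What to change.** In SAP 7.6.2.3 and 8.3, state that cGFR is set to 0 at every analysis time point on or after the date of graft loss or death, whether or not a creatinine result exists. Two details make this programmable. First, a result drawn on or after that date should not be used as measured in any window. Second, the SAP should say which date counts as the graft-loss date under the dialysis criterion, because protocol 5.3.12 gives a duration but no date.

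Flag and list cGFR values drawn during dialysis before the graft-loss criteria are met. Keep them in the analysis and do not set them to missing.

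The cost is a sentence or two in the SAP and one programming condition on dates that the graft-loss definition already needs. No new data and no change in sample size are required. The downside is that a few measured values are no longer used.

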7.6.2.4 Donor Specific Antibodies

The percentage of subjects with detectable DSA on Day 1, and of *de novo* DSA at 12 and 24 months post-transplant will be descriptively summarized by treatment group. The data from the DSA assessments will be cross-matched with the number of donor/recipient HLA mismatches to confirm the anti-donor status of any detected anti-HLA antibodies. The results will be categorized according to the results obtained by flow cytometry, as follows:

- Median fluorescence intensity(MFI) > 2000 = Positive.
- MFI 1000-2000 = Potentially Positive.

- $MFI < 1000 = \text{Negative}$.

7.6.2.5 Cardiovascular and Metabolic Co-Morbidities

Blood pressure

Descriptive summaries of SBP and DBP will be provided by treatment group at Months 3, 6, 12, and 24. In addition, the changes from baseline (last measurement prior to transplant) to the subsequent measurements obtained at each subsequent (post-transplant) time points will be summarized.

Percentage of patients in each treatment group with blood pressures above the values given below will be presented in a table to include results pre-transplant and at each subsequent Study Visit:

- > 130/80mmHg (pre-hypertension).
- > 140/90mmHg (hypertension).

Descriptive statistics regarding the number of antihypertensive medications received in each group at 6, 12 and 24 months will be provided to evaluate severity of hypertension per the protocol definition (e.g. mean/median number of antihypertensive medications).

Lipids

Descriptive summaries of fasting lipid parameters (total cholesterol, HDL cholesterol, LDL cholesterol and TG) at Months 3, 6, 12, and 24 will be presented. Changes from baseline values (last measurement prior to transplantation) for each of the fasting lipid parameters (total cholesterol, HDL cholesterol, LDL cholesterol and TG) to Month 12 and Month 24 will be descriptively summarized.

Descriptive statistics regarding the number of lipid-lowering medications received in each group at 6, 12 and 24 months will be provided (e.g. mean/median number of lipid-lowering medications).

Control of fasting blood glucose

Mean values and changes from baseline (last measurement prior to transplantation) in fasting blood glucose and HbA1C levels to Month 6, Month 12 and Month 24 will be descriptively summarized.

New Onset Diabetes Mellitus After Transplantation (NODAT)

The incidence of NODAT at 6, 12, and 24 months post-transplantation will be summarized along with the corresponding 95% CIs within each treatment regimen group.

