### **5.3.14     *Diagnosis and Treatment of Hypertension***

Hypertension will be evaluated, defined and treated in this protocol according to the Seventh Report of the Joint National Committee on the Prevention, Detection, Evaluation, and Treatment of High Blood Pressure guidelines for subjects with renal transplants. Accordingly, in adults, pre-hypertension is defined as SBP  $\geq 130$  mm Hg or DBP  $\geq 80$  mm Hg, and hypertension as SBP  $\geq 140$  mm Hg or DBP  $\geq 90$  mm Hg. In addition, subjects who do not meet these levels of SBP or DBP, but are receiving medication(s) for the management of hypertension, and/or those with a prior medical history of hypertension, are also to be considered as having hypertension.

Per the guidelines included in the *Seventh Report of the Joint National Committee on the Prevention, Detection, Evaluation, and Treatment of High Blood Pressure* in the absence of compelling data for renal transplant recipients, no particular class of antihypertensive drugs can be considered superior to any other. Therefore, subjects should be treated per the investigator's discretion and in accordance with local standards of care to reach the target blood pressure goals.

The intensity of an anti-hypertensive treatment regimen is defined as the total number of antihypertensive medications used to control hypertension. In subjects with hypertension, whether adequately controlled or not, all antihypertensive medications will be counted in determining the presence of hypertension and the intensity of the treatment regimen, since the antihypertensive effects will be considered present regardless of the ostensible indication for which they were prescribed.

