- 9) The summary of median fluorescence intensity (MFI) of anti-HLA donor specific antibodies will not be produced. Instead, the number of subjects with DSA will be summarized.
- 10) Analysis of anti-viral T-cell responses will not be provided. The immune cell phenotypes will be summarized for all subjects and by acute rejection status (subjects experiencing at least one acute rejection vs those without any acute rejection). A corresponding listing will be provided.
- 11) The patterns of protein excretion, by urinary proteomics will be summarized for all subjects and by acute rejection status (subjects experiencing at least one acute rejection vs those without any acute rejection). Proteins that are below LLOQ in more than 50% of samples will not be analyzed. A corresponding listing will be provided.

Due to the fact that some data were not collected, the following analyses cannot be produced:

- 1) Clinically significant changes in vital signs were not collected. Thus, they will not be summarized. Instead, a summary of the number of subjects with systolic or diastolic blood pressure values above the values mentioned in [section 7.6.2.5](#) will be provided. Also, investigators may have reported corresponding adverse events which will be summarized and listed as described in [Section 7.7](#).
- 2) For the analysis of any clinical consequences of CSBPAR, and associated changes in the expression of exploratory gene sets associated with acute rejection, no summary or listing that includes gene expression will be provided.
- 3) The analysis on titers of DSA and of the characterization of any de novo DSA detected by IgM and IgG classes, and by the presence or absence of complement fixing properties will not be produced. Instead, the number of subjects with DSA will be summarized.
- 4) The IHC analyses of any remaining allograft biopsy tissue samples available at sites following clinical review will not be provided, as no such residual tissue samples were submitted for this purpose.

The following analyses will not be provided as part of this analysis plan:

- 1) The analyses related to anti-viral T-cell responses and mean percent change in anti-viral T cell responses will not be produced as part of the analyses described in this analysis plan. If they are to be performed subsequently, they will be described in a separate analysis plan.

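### The SAP rows labelled pre-hypertension and hypertension use a narrower rule than the protocol, so the hypertension row can equal or understate, but never exceed, protocol-defined hypertension

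*SAP*

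**What the plan says.** **SAP 7.6.2.5 (Cardiovascular and Metabolic Co-Morbidities).** "Percentage of patients in each treatment group with blood pressures above the values given below will be presented in a table", before transplant and at each later visit. The two cut-offs are "> 130/80mmHg (pre-hypertension" and "> 140/90mmHg (hypertension", each carrying its diagnostic label. The rule uses readings only. The number of antihypertensive drugs is summarised separately at 6, 12 and 24 months, as a measure of severity.

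**SAP 7.1 (Modifications to the Analyses).** Clinically significant vital-sign changes were not collected. In their place the SAP gives "a summary of the number of subjects with systolic or diastolic blood pressure values above the values mentioned in" section 7.6.2.5.

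**Protocol 5.3.14 (Diagnosis and Treatment of Hypertension).** Pre-hypertension is SBP ≥130 or DBP ≥80; hypertension is SBP ≥140 or DBP ≥90. Subjects below these levels but "receiving medication(s) for the management of hypertension, and/or those with a prior medical history of hypertension, are also to be considered as having hypertension". The section adds that, in subjects with hypertension, controlled or not, "all antihypertensive medications will be counted in determining the presence of hypertension and the intensity of the treatment regimen".

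**The concern.** Two rules sit under one label. A reading of exactly 140 or 90 is hypertensive by the protocol but not by the SAP row, unless the other component exceeds its cut-off. A patient whose pressure is controlled by drugs is likewise hypertensive by the protocol and absent from the row, as is a patient with a history of hypertension and normal readings now. The pre-hypertension row shares the inequality mismatch.

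The table supports the secondary objective on cardiovascular co-morbidities and stands in for the uncollected vital-sign changes. A reader of the study report who knows the protocol definition would take the row as the share of patients with hypertension, when it is the share with a high reading at that visit. A patient brought below the cut-off by treatment would appear to leave the hypertension category.

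**Working it through.** The plan states no figure for this table, so there is nothing to reproduce. The check compares the two rules and then illustrates the possible size.

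**1. The rules as sets**

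- SAP: A = {SBP > 140 or DBP > 90}. The 'or' comes from SAP 7.1.
- Protocol: B = {SBP ≥ 140 or DBP ≥ 90 or on antihypertensive medication or prior hypertension}.

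Every member of A belongs to B, so P(A) ≤ P(B) in any data set.

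**2. Enumeration**

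Take every whole-number SBP from 90 to 199 and DBP from 50 to 119, crossed with treated yes/no and history yes/no.

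- Profiles in A but not in B: 0.
- Profiles outside A: SBP 90–140 (51 values) × DBP 50–90 (41 values) × 4 = 8,364.
- Of these, also outside B: SBP 90–139 (50) × DBP 50–89 (40) × 1 (untreated, no history) = 2,000.
- In B but not in A: 8,364 − 2,000 = 6,364.

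The 6,364 split into 364 with a reading on the boundary (91 pairs × 4) and 6,000 below it that qualify only through treatment or history (2,000 × 3). These are unweighted profiles, not patients; they establish direction, not size.

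**3. Illustration of > versus ≥**

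None of these inputs is in the documents: bivariate normal readings, SD 16 (SBP) and 10 (DBP), correlation 0.6, two pairs of means, and three levels of rounding in recording. One million pairs were simulated per pair of means.

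| Mean SBP/DBP | Recorded to | > (SAP) | ≥ | Difference, points |
|---|---|---|---|---|
| 130/78 | 1 mmHg | 28.9% | 31.5% | 2.6 |
| 130/78 | 2 mmHg | 27.6% | 32.9% | 5.3 |
| 130/78 | 10 mmHg | 18.9% | 44.8% | 25.9 |
| 138/82 | 1 mmHg | 47.8% | 50.8% | 3.0 |
| 138/82 | 2 mmHg | 46.3% | 52.3% | 6.0 |
| 138/82 | 10 mmHg | 35.2% | 64.4% | 29.2 |

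With 35 per group (SAP 6.1) and 1-mmHg recording, the inequality moves about one patient: 35 × 0.289 = 10.1 against 35 × 0.315 = 11.0, or 35 × 0.478 = 16.7 against 35 × 0.508 = 17.8.

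**4. Illustration of treatment and history**

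Let g be the ≥ percentage and u the assumed share treated or with a history, independent of the reading. The protocol percentage is g + (1 − g)u. With 1-mmHg recording, g is 0.315 or 0.508:

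- u = 0.3: 0.315 + 0.685 × 0.3 ≈ 52%; 0.508 + 0.492 × 0.3 ≈ 66%.
- u = 0.6: about 73% and 80%.
- u = 0.9: about 93% and 95%.

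The SAP row stays at 29% and 48% throughout. Unless readings are heavily rounded, omitting treated and history-positive subjects matters more than the inequality.

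**The case against.** The strongest reply is that the table is a summary of exceedance, not of diagnosis. It is introduced as patients above stated values, visit by visit. For following measured pressure over time a reading-only rule is legitimate, and arguably better: a history criterion counts the same patients at every visit and cannot show change. At u = 0.9 above, a protocol-defined row would sit at 93–95% with little room to differ between arms. This stands as a defence of the rule. It does not defend the label, which borrows a term the protocol defines otherwise, or the strict inequality, which serves no stated purpose.

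Four stronger readings are tempting, and the documents do not support them.

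- *The slash means both components must exceed.* SAP 7.1 says systolic or diastolic, so the connector is settled.
- *The table hides a difference between arms in drug treatment.* SAP 7.6.2.5 reports the number of antihypertensive drugs by group at Months 6, 12 and 24, and protocol 8.4.2.5 also plans summaries of antihypertensive therapy. The row understates hypertension; the difference in drug use remains visible elsewhere.
- *A secondary endpoint is miscounted.* The listed blood pressure endpoints are SBP and DBP values and mean changes. Hypertension incidence is not listed, whereas new-onset diabetes incidence is.
- *SAP 7.1 conceals a changed analysis.* Protocol 8.4.2.5 plans no table of the percentage hypertensive, so no planned analysis was altered, and SAP 7.1 openly introduces the table as a substitute.

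**Conclusion.** The point holds as a minor inconsistency of rule and label. That the SAP hypertension row can only equal or fall below protocol-defined hypertension follows from the two definitions and needs no assumption. Its size cannot be obtained from the documents. Under the assumed distributions the inequality alone costs about 3 points with 1-mmHg recording, roughly one patient per group of 35. The 26 to 29 points seen with rounding to 10 mmHg should not be relied on, because nothing in the documents suggests such rounding. The treatment and history component depends entirely on how many patients qualify that way, which the documents do not state.

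The consequence is limited to one descriptive table; SAP 7.2 rules out statistical tests. No primary or listed secondary endpoint changes.

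**What to change.** In SAP 7.6.2.5:

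1. Write the cut-offs as SBP ≥130 or DBP ≥80, and SBP ≥140 or DBP ≥90, matching protocol 5.3.14.
2. Label these rows as measured blood pressure at or above the cut-off, without the diagnostic terms.
3. If any row is to be called hypertension, add one on the protocol 5.3.14 definition, split into reading, on medication and prior history. The split keeps the row informative when most patients qualify through history.

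This aligns the table with the protocol's own definition and takes no view on which blood pressure definition is clinically right.

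The cost is SAP wording and one extra row with its split. No new data are needed: medical history is taken at screening, concomitant medication is reviewed at visits, and blood pressure is measured under the protocol schedule. The downside is that the added row may change little over visits if prior hypertension is common.
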